### 13.2.2. Duration of Response (DOR)

Duration of response for subjects with CR or PR is defined as the date of first qualifying response (CR or PR) until the date of PD or death, whichever is earliest.

$$DOR \text{ (weeks)} = \frac{([Date \text{ of } PD \text{ or } Death - Date \text{ of First CR or PR}] + 1)}{7}$$

For subjects who have neither progressed nor died, DOR will be censored at the date of the last evaluable disease assessment. The median DOR will be estimated using Kaplan-Meier methods and summarized.

Separate Kaplan-Meier plots for subjects enrolled to Parts 1, 2A, and 2B will be provided.

### **13.2.3. Progression-Free Survival (PFS)**

PFS is defined as the date of initiation of KZR-261 until the date of documented PD or death from any cause, whichever occurs first.

$$PFS \text{ (weeks)} = \frac{([Date \text{ of } PD \text{ or } Death - Date \text{ of } First \text{ Dose} \text{ of } KZR - 261] + 1)}{7}$$

For subjects who have neither progressed nor died, PFS will be censored at the date of the last evaluable disease assessment. The median PFS will be estimated using Kaplan-Meier methods and summarized.

Progression-Free Survival at 4 months (PFS4) is defined as the percentage of subjects alive and progression-free at 4 months (ie, 17 weeks) after the initiation of study treatment. The PFS4 responders will be summarized using frequencies and percentages. Similar to analysis of ORR, two-sided 90% CIs for PFS4 responders using the Clopper-Pearson approach will be calculated.

Progression-Free Survival at 6 months (PFS6) is defined as the percentage of subjects alive and progression-free at 6 months (ie, 26 weeks) after the initiation of study treatment. The PFS6 responders will be summarized using frequencies and percentages. Similar to analysis of ORR, two-sided 90% CIs for PFS6 responders using the Clopper-Pearson approach will be calculated.

Separate Kaplan-Meier plots for subjects enrolled to Parts 1, 2A, and 2B will be provided.

### **13.2.4. Overall Survival (OS)**

OS is defined as the date of first dose of KZR-261 until the date of death from any cause.

$$OS \text{ (weeks)} = \frac{([Date \text{ of } Death - Date \text{ of } First \text{ Dose} \text{ of } KZR - 261] + 1)}{7}$$

For subjects who have not died, OS will be censored at the date the subject is last known to be alive or the date of last contact, whichever is later. The median OS will be estimated using Kaplan-Meier methods.

Separate Kaplan-Meier plots for subjects enrolled to Parts 1, 2A, and 2B will be provided.

### **13.2.5. Clinical Benefit Rate (CBR)**

Clinical benefit is defined as achieving a best response of CR, PR, or SD over 2 or more response assessment timepoints. Subjects meeting the criteria for clinical benefit will be summarized using frequencies and percentages. Like analysis of ORR, two-sided 90% CI using the Clopper-Pearson approach will be calculated.

### **13.2.6. Prostate-Specific Antigen Doubling Time**

Prostate-specific antigen doubling time (PSADT) may be calculated using a published method ([Scher et al., 2016](#)).

### **13.2.7. Percentage Change from Baseline in Sum of Diameters of Target Lesions**

Best percentage change from baseline in the sum of longest diameters of target lesions will be summarized descriptively by dose level among subjects enrolled to Part 1 and tumor cohort for Part 2A and 2B subjects. Best percentage change from baseline in sum of longest diameters will

be presented in a Waterfall Plot with corresponding dose level, best overall response, and primary cancer diagnosis identified. Individual percentage changes from baseline in sum of diameters of target lesions overtime will be presented in a spider plot with treatment identified. Scatter plot and dose response curve based on E-max model in percentage change from baseline in sum of diameters of target lesions will also be provided.

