3. STUDY DESIGN

3.1. Overview of Study Design

This FIH, open-label, multicenter, Phase 1 study is designed to assess the safety and tolerability, preliminary anti-tumor activity, and the PK characteristics of KZR-261, as well as identify the RP2D. KZR-261 will be administered as a 30- to 60-minute IV infusion via a central line on Days 1, 8, and 15 of a 4-week (28-day) treatment cycle. (Doses may be held up to 7 days for resolution of non-DLT toxicity.) Eligible subjects will have locally advanced or metastatic solid malignancies and no approved therapies, or refused such therapies if available.

The study will be conducted in 2 parts: Part 1 (Dose Escalation) and Part 2 (Part 2A –Dose Expansion and Part 2B – Dose Optimization).

[figure not shown]
In Part 1, increasing doses of KZR-261 will be administered in an “i3+3” design to approximately 70 subjects to evaluate the safety and tolerability, PK, and pharmacodynamics of KZR-261, including identifying the MTD or MAD.

The Dose Expansion phase will commence following determination of the MTD/MAD and a review of the totality of safety data from Part 1. Part 2A will further characterize the safety profile of KZR-261 at the MTD or MAD and evaluate the anti-tumor activity of KZR-261 in subjects who have select malignancies. Up to 175 subjects may be enrolled in up to 4 tumor-specific cohorts (such as malignant melanoma [including uveal melanoma], mesothelioma, mCRPC, and mCRC) and 1 “All-Tumors” cohort. Additional or different tumor-specific cohorts may be investigated at the Sponsor’s discretion. Each tumor-specific cohort will enroll 15 subjects during Stage 1, expanding up to 35 subjects (Stage 2) as defined by a prespecified futility analysis and if the tumor type is not selected for investigation in Part 2B (see below). If futility is not rejected after Stage 1 (ie, prespecified criteria for futility are met), subsequent enrollment to that Part 2A cohort will cease. The All-Tumors cohort may enroll up to 35 biopsy-evaluable subjects.

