If a slot within the current dose escalation cohort is not available, additional subjects may be treated at a lower dose level deemed by the SRC to be safe and adequately tolerated. Subjects with malignant melanoma, malignant mesothelioma, mCRPC, or mCRC are preferred but not required for backfilling.

The SRC can recommend enrollment of additional subjects at the putative MTD or MAD dose level to further assess safety at this dose.

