10.5.5. Anti-tumor Activity

ORR is defined as the proportion of subjects achieving a best response of CR or PR according to RECIST v1.1. CBR is defined as the proportion of subjects achieving a best response of CR/PR or stable disease over a period of ≥ 2 consecutive response assessment time points. Subjects with mCRPC will be assessed for response/clinical benefit per PCWG3 guidelines. DOR is defined as the date from first occurrence of CR or PR to the date of documented PD or death. In assessing DOR, a subject alive and without disease progression will be censored at the date of the last evaluable disease assessment. PFS is defined as the date of initiation of study treatment to the date of documented PD or death from any cause, whichever occurs first. OS is defined as the date of initiation of study treatment to the date of death from any cause.

The 2-sided exact CI using the Clopper-Pearson method will be calculated for response/clinical benefit rates where applicable ([Clopper and Pearson, 1934](#)). Distributions for PFS, DOR, and OS will be estimated by Kaplan-Meier methodology.

The CBR will be summarized by response assessment timepoints (ie, every 2 cycles).

Summary tables of best ORR, PFS, and OS will be provided overall and by malignancy if necessary. Efficacy listings will be provided that include best response, first CR/PR date, last date with CR or PR, most recent date without progression, progression date, death date, and last tumor assessment date, etc. The definition of each response category is provided in RECIST v1.1.

[Table 12](#) provides an overview of the planned efficacy analysis.

Table 12: Anti-tumor Assessments

Endpoint	Analysis Sets	Statistical Method
Objective response rate (ORR)	Dose Expansion and Optimization cohorts	Exact CI
Progression-free survival (PFS)	Dose Expansion and Optimization cohorts	Kaplan-Meier
Duration of response (DOR)	Dose Expansion and Optimization cohorts	Kaplan-Meier
Overall survival (OS)	Dose Expansion and Optimization cohorts	Kaplan-Meier
Clinical benefit rate (CBR)	Dose Expansion and Optimization cohorts	Exact CI

CI=confidence interval.

Note: Anti-tumor analyses may include patients in dose escalation phase.

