### **7.4. Data Analysis Conventions**

All data analysis will be performed by [REDACTED] after the study is completed and the database has been locked. Statistical programming and analyses will be performed using SAS® version 9.4 or higher. Output will be provided in rich text format (RTF) for tables and portable document format (PDF) for tables, listings, and figures using landscape orientation. All study data will be listed by subject, dose level in Part 1 (Dose Escalation) and cohort in Part 2A and 2B (Tumor-Specific Dose Expansion and Dose Optimization), and visit (as applicable) based on all enrolled subjects unless otherwise specified. Listings will be sorted by dose level in Part 1 (Dose Escalation) and by cohort in Part 2A (Tumor-Specific Dose Expansion) and Part 2B (Dose Optimization), subject number, visit/time point, and parameter as applicable.

Summaries for continuous and ordinal variables will include the number of observations (n), arithmetic mean, standard deviation, median, minimum, and maximum. Minima and maxima will be reported with the same precision as the raw values; means and medians will be presented to one additional decimal place than reported in the raw values. Standard deviations will be presented to two additional decimal places than reported in the raw values. Summaries for discrete variables will include counts and percentages. All percentages will be rounded to one decimal place (ie, XX.X%). Changes from baseline will be calculated as follow-up visit minus baseline.

Unless otherwise specified, all data will be summarized by dose level and overall, for Part 1 (Dose Escalation), tumor-specific cohort for Part 2A (Dose Expansion), and dose and tumor-specific cohort for Part 2B (Dose Optimization).

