## 13. EFFICACY ANALYSES

All efficacy analyses will be performed on the Response Evaluable Population.

All efficacy data will be listed and summarized with descriptive statistics.

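### SAP 13.2.7 leaves the E-max tumor-shrinkage curve free to pool study parts without a tumor-type term, which would confound dose with tumor type

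*SAP*

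**What the plan says.** The model gets one sentence in SAP 13.2.7, which promises a "Scatter plot and dose response curve based on E-max model in percentage change from baseline in sum of diameters of target lesions". It gives no equation, covariate, study part, dose variable or time point. Earlier in the section, best percentage change is "summarized descriptively by dose level among subjects enrolled to Part 1 and tumor cohort for Part 2A and 2B subjects". The waterfall plot must show dose level and primary diagnosis; nothing similar is asked of the fitted curve.

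Other passages bear on who enters the fit:

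- SAP 13: "All efficacy analyses will be performed on the Response Evaluable Population". SAP 6.2 defines that population without reference to study part.
- Protocol 10.5.5, note to Table 12: "Anti-tumor analyses may include patients in dose escalation phase". No rule for combining them is given.
- SAP 13.2.3, on PFS: "Separate Kaplan-Meier plots for subjects enrolled to Parts 1, 2A, and 2B will be provided". The sections on DOR and OS say the same.
- SAP 7.4 sets a default that individual sections may override. It reads in part: "all data will be summarized by dose level and overall, for Part 1 (Dose Escalation), tumor-specific cohort for Part 2A (Dose Expansion". For Part 2B the default uses both the dose and the tumor cohort.

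On design, Protocol 3.1 states that "Part 2A will further characterize the safety profile of KZR-261 at the MTD or MAD", and SAP 4.1.2 gives that dose or one recommended by the SRC. Part 2A may reach 175 subjects: four tumor-specific cohorts of 35 and an All-Tumors cohort of 35. Part 1 plans about 70 subjects, and SAP Table 2 lists nine doses from 1.8 to 80 mg/m2. Part 2B randomizes 1:1 between two doses within tumor type.

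**The concern.** A dose-response curve is interpretable only if subjects at low and high doses are otherwise comparable. If the parts are pooled here, they are not. Doses below the MTD/MAD come mainly from Part 1, which is open to solid tumors generally. The MTD/MAD gains up to 140 subjects in four tumor types chosen partly for predicted sensitivity (Protocol 1.2.1 and 1.2.2). If those types change in size differently from the rest at any dose, a model without a tumor term attributes the difference to dose.

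This is the only dose-efficacy model that the SAP itself describes. Protocol 3.2.4 makes anti-tumor effect at a lower dose a reason to prefer a lower dose in Part 2, so a curve made steeper or flatter by tumor mix could mislead that discussion. In addition, SAP 13.2.7 summarizes Part 2B shrinkage by tumor cohort alone. That overrides the SAP 7.4 default and drops the randomized dose contrast from the summary.

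**Working it through.** The documents give no size, SD or effect for this curve, so there is no stated figure to reproduce. The check asks what a pooled fit shows when dose truly has no effect.

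**From the documents:** dose levels (SAP Table 2); about 70 subjects in Part 1, with 6 to about 12 at the putative MTD/MAD; 4 × 35 + 35 = 175 in Part 2A; 4 × 15 = 60 tumor-specific subjects if all cohorts stop at Stage 1; 4 × 30 = 120 in Part 2B.

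**Assumed:** top dose 60 mg/m2 (27 as an alternative); SD 30 points; 30% of Part 1 in selected types at every dose; selected types shrinking δ points more at every dose; All-Tumors subjects counted as other types.

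**Step 1: tumor mix by dose.** With a top dose of 60 there are eight Part 1 levels. Seven subjects each plus 12 extra at the top gives 8 × 7 + 12 = 68, with 19 at the top. Let S be the selected-type subjects in Part 2A, A the All-Tumors subjects and f the selected share in Part 1.

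Share at top dose = (S + 19f) / (S + A + 19); share below = f; crude false effect = -δ × (difference in shares).

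- Full Part 2A: (140 + 5.7) / 194 = 0.751. Difference from 0.30 = 0.451. Crude effect -4.5 points at δ = 10 and -9.0 at δ = 20.
- Stage 1 only: (60 + 5.7) / 114 = 0.576. Difference 0.276. Crude effect -2.8 and -5.5.
- Full Part 2A, f = 0.60: (140 + 11.4) / 194 = 0.780. Difference 0.180. Crude effect -1.8 and -3.6.

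**Step 2: the fitted curve.** E-max was fitted by least squares over an ED50 grid of 0.5 to 160 mg/m2, with 3,000 simulated data sets per setting and zero true dose effect. Entries are the mean fitted difference, top minus lowest dose, in percentage points; negative means apparently more shrinkage at the top dose.

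| Pooled fit, no tumor term | δ = 5 | δ = 10 | δ = 20 |
|---|---|---|---|
| Full 175, top dose 60 | -3.4 | -6.6 | -12.3 |
| Full 175, top dose 27 | -3.3 | -6.0 | -12.0 |
| Stage 1 only (60 + 35) | -2.0 | -3.9 | -7.6 |
| Full 175, almost no selected types in Part 1 | -5.2 | -10.0 | -18.4 |
| Full 175, 60% selected types in Part 1 | -1.2 | -2.6 | -5.1 |
| Stage 1 plus Part 2B (120, at 60 and 40) | -3.0 | -6.8 | -13.1 |

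These exceed the crude effects where both were worked out. A smooth curve spreads a step at the top dose over the whole range, so its value at the lowest dose is pulled away from the lower-dose average.

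**Step 3: alternatives on the same data.** With a selected-versus-other tumor term, the mean false effect lay between -0.4 and 0.3 points in every setting. Using Part 1 only, it lay between -0.5 and 0.5.

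**Step 4: visibility.** The plan has no test. As a gauge, a 5%-level comparison with a flat line, in the first row of the table, called a dose response in 5.6%, 11.9% and 32.7% of runs at δ = 5, 10 and 20. At δ = 10 and 20 the tumor-adjusted fit gave 3.9% and 4.2%, and Part 1 only gave 5.3% and 5.7%.

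**The case against.** A reader might infer that the SAP plans one curve through all parts and will therefore show a false dose response. The documents do not support that. SAP 13.2.7 splits its own descriptive summary by part, SAP 7.4 does so by default, and the Table 12 note says only that escalation patients may be included. Part 2A has a single planned dose, so Part 1 is the natural basis for a curve over many doses, and a Part 1-only fit showed no bias. This stands: pooling is left open, not specified. But SAP 7.4 governs how data are summarized, not what a model is fitted to, and the SAP states a split by part for the Kaplan-Meier plots. Two analysts could follow the text and draw different curves.

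Other points also stand:

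- Backfill reduces the confounding. Selected types entering at lower doses ("Subjects with malignant melanoma, malignant mesothelioma, mCRPC, or mCRC are preferred but not required for backfilling") even out the mix. It is a preference, so it cannot be relied on to remove the imbalance.
- The selected types need not shrink more. Selection also used nonclinical data and unmet need, and the same bioinformatics flagged several types assigned to All-Tumors. No tumor-type difference appears in the documents.
- The full 175 is a ceiling. It requires every cohort to pass futility and none to move to Part 2B.
- The tumor term works fully here because the simulated difference is the same at every dose. If tumor types differ in the steepness of their response, an additive term will not remove everything.
- No decision rule cites the curve. The RP2D rests on the totality of results, and separate PK and pharmacodynamic plans were not available.

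**Conclusion.** The concern holds in a limited form. The text permits a pooled, unadjusted E-max curve, and such a curve would confound dose with tumor type. Under the main assumptions (full Part 2A, top dose 60 mg/m2, SD 30, 30% selected types in Part 1), a 10- to 20-point tumor difference produces about -6.6 to -12.3 points of apparent dose effect where none exists. If Part 2A stops at Stage 1, the range is -3.9 to -7.6. The distortion is small at a 5-point difference or when about 60% of Part 1 is already in selected types. It is absent in a Part 1-only fit, given a similar tumor mix across Part 1 doses.

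It would be too strong to say that the curve necessarily favors the higher dose. The sign follows the tumor difference: if the selected types shrink less, the bias reverses and could hide a real dose response. Nor is an error rate at stake, since the curve is descriptive. The harm is a misleading figure in RP2D or dose-optimization discussion. Because SD, tumor difference, top dose and tumor mix are all assumed, the figures show direction and rough size only.

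**What to change.** In SAP 13.2.7:

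1. State which study parts feed the E-max curve.
2. If parts are pooled, include a tumor-type term (the tumor-specific types and other), assigned by diagnosis whatever the study part, and show the Part 1-only curve as a sensitivity plot.
3. Summarize Part 2B percentage change by randomized dose within tumor cohort instead of by tumor cohort alone, in line with SAP 7.4. This contrast does not depend on the additive form of the tumor term.

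The cost is SAP wording and a few model parameters on data already collected. The downside is a slightly wider interval around the curve.

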## **14. EXPLORATORY ANALYSES**

Assessments of various pharmacodynamic study readouts as a function of dose and time post-administration may be described and related to efficacy metrics (eg, overall response, DOR, PFS), PK, and safety parameters.

Details of the planned exploratory analysis will be described in a separate Pharmacodynamic Analysis Plan.

## **15. SAFETY ANALYSES**

All safety analyses will be conducted using the Safety Population.

### **15.1. Adverse Events**

An AE is defined as any untoward medical occurrence in a clinical study subject administered a medicinal product, which does not necessarily have a causal relationship with this treatment. An AE can therefore be any unfavorable and unintended sign (including an abnormal laboratory finding), symptom, or disease temporally associated with the use of a medicinal (investigational) product, whether or not it is related to the medicinal (investigational) product. This includes an exacerbation of pre-existing conditions or events, intercurrent illnesses, drug interaction or the significant worsening of the indication under investigation that is not recorded elsewhere in the eCRF under specific efficacy assessments. Anticipated fluctuations of pre-existing conditions, including the disease under study, that do not represent a clinically significant exacerbation or worsening need not be considered AEs.

It is the responsibility of the Investigator to document all AEs that occur during the study. AEs will be elicited by asking the subject a nonleading question, for example, “Have you experienced any new or changed symptoms since we last asked/since your last visit?” AEs should be reported on the appropriate page of the eCRF. All AEs will be coded using the MedDRA Version 26.0 or later.

TEAEs are defined as an event that occurred from the date of the first dose of KZR-261 administration and continuing for 30 days following the last dose administration and will include AEs that emerged during treatment having been absent pre-treatment, or worsened relative to the pre-treatment state. Adverse events recorded in the eCRF which began prior to treatment will not be included in the summary tables but will be included in the AE data listings.

Severity of AEs will be graded according to NCI CTCAE Version 5.0. If there is a change in severity of an AE, it must be recorded as a separate event. For AEs not listed in the NCI CTCAE, the Investigator should determine the severity of the AE according to the criteria in [Table 5](#).

**Table 5: NCI CTCAE Adverse Event Severity Grades**

Grade 1 (Mild)	Mild; asymptomatic or mild symptoms; clinical or diagnostic observations only; intervention not indicated.
Grade 2 (Moderate)	Moderate; minimal, local or noninvasive intervention indicated; limiting age-appropriate instrumental activities of daily living.
Grade 3 (Severe)	Severe or medically significant but not immediately life-threatening; hospitalization or prolongation of hospitalization indicated; disabling; limiting self-care activities of daily living.
Grade 4 (Life-threatening)	Life-threatening consequences; urgent intervention indicated.
Grade 5 (Death)	Death related to the adverse event.

The Investigator will assess the causal relationship between study drug and an AE. All AEs will be deemed related to study drug unless irrefutably determined to be related to the disease under study or another non-study drug cause.

The causal relationship between the study drug and the AE will be assessed using one of the following two categories:

1. Unrelated: An AE is not associated with study drug if any of the following is true:
  - A temporal relationship is lacking (ie, the event did not occur within a reasonable time frame after administration of the study drug).
  - Other causative factors more likely explain the event (eg, intercurrent illness, concomitant treatments, traumatic event).
  - The AE did not reoccur upon re-administration of the study drug (if applicable).
2. Related: An AE is attributed to the study drug if any of the following is true:
  - There is a positive temporal relationship (ie, the event occurred within a reasonable time frame after administration of study drug).
  - The AE is more likely explained by the study drug than by another cause and cannot be clearly assessed as “unrelated”.

An overall summary that includes the number and percentage of subjects who experienced at least one TEAE, including treatment-related TEAEs, SAEs, treatment-related SAEs, TEAEs leading to treatment interruption, dose reduction, discontinuation, death, and Grade 3 or 4 TEAEs will be provided. TEAEs will be summarized by dose level in Part 1 (Dose Escalation) and by tumor cohort in Parts 2A and 2B (Tumor-Specific Dose Expansion and Dose Optimization) All verbatim TEAEs will be coded to a MedDRA system organ class (SOC) and preferred term (PT). If a subject reports the same PT multiple times within a SOC, that PT will be counted once (at the highest level of severity) within that SOC. If a subject reports multiple different PTs within the same SOC, a subject will be counted once at the SOC level. SOCs and PTs will be listed in order of descending frequency within each SOC.

Summaries of TEAEs by maximal severity will be presented.

All AEs will be presented in a subject listing.

The following will be presented as listings and summary tables:

- TEAEs leading to study treatment discontinuation
- TEAEs related to KZR-261
- TESAEs
- TESAEs related to KZR-261
- TEAEs related to KZR-261 leading to early treatment discontinuation
- TEAEs leading to dose reduction
- TEAEs leading to death by category (Death on-treatment, Death post-treatment, and all death)
- TEAEs related to KZR-261 leading to death
- Grade 3 or 4 TEAEs
- Grade 3 or 4 TEAEs related to KZR-261
- Selected TEAEs by category (such as neutropenia and neutrophil count decreased, QTc prolongation and cardiac toxicities, liver toxicity, nephrotoxicity, bone marrow toxicity, etc)

In addition, all SAEs will be presented in a separate listing.

